7.3 Duration of Study

It is anticipated that the total duration of the study will last approximately 72 months (60 months for recruitment and a minimum of 12 months of follow-up per individual). Patients

may be followed for up to 3 years.

7.4 Duration of Follow Up

Patients will remain enrolled on this protocol until there is evidence that their disease has progressed either locally or distantly; or until study withdrawal for any reason. These patients will be followed for survival.

Progression may be determined by imaging or clinical criteria, i.e., increasing ascites and cachexia. We estimate that most patients will remain a subject in this study for approximately one year. Schedule of follow-up will be as according to the Study Calendar in Section 14.

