7.2 Follow-up

All patients will be monitored with clinic visits, labs, and serial imaging (CT or MR scans and PET/CT if possible), and other tests as needed.

Patients deemed resectable at any time during follow-up may proceed to surgery. These patients will be withdrawn from the protocol and followed for survival.

Patients will have consultations in the first year every three months following study treatment as defined in the Study Calendar (Section 14); a follow up at 4-6 weeks is optional and may be done to assess subject's resectability, or if clinically indicated by study PIs or patient's treating physician.

For years 2 and 3, follow-up is recommended every 6 months, or until death or study withdrawal (due to progression, patient withdrawal, or noncompliance as defined in Section 7.5 Criteria for Removal from Study). Follow up intervals may be more frequent as indicated clinically. In the event of intolerable toxicity from mFFX, subjects will still be followed per protocol although chemotherapy may be altered or discontinued, the decisions of which will be left to the treating Medical Oncologist. Visits should include:

- Consultation with physical examination
- Labs: CBC, CMP, CA199. CEA and research bloods are optional.
- Scans: CT or MR and PET/CT if possible (PET/CT is recommended at 3 month follow-up visit but is not required)
- QOL (Quality of Life) Assessment with EORTC QLQ C-30 / PAN26 survey
- Adverse Event (AE) evaluation
- Concomitant Medications: PPIs and pain medications as applicable
- Other tests as appropriate.

Patients who remain on-study will be followed until death and cause of death should be obtained when possible.

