7.5 Criteria for Removal from Study

Patients will be withdrawn from the study for any of the following reasons:

- disease progression (as defined in Section 15.1.2 Disease Parameters)
- patient withdrawal
- pregnancy
- patient noncompliance, or failure of the patient to follow instructions of the study staff
- protocol director decides that continuing participation could be harmful to the patient
- treatment needed for patient that is not allowed in the study
- patient is deemed resectable and proceeds to surgery
- study cancellation
- other administrative reasons
- unanticipated circumstances.

Patients will continue mFFX on-study until one of these endpoints; in the event of intolerable toxicity from mFFX, subjects will still be followed per protocol although chemotherapy may be altered or discontinued, the decisions of which will be left to the treating Medical Oncologist.

Patients withdrawn from the study will be followed for overall survival only.

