15.1.5 Progression-Free Survival (or other time-to-event parameters)

The criteria for time to progression and progression-free survival (PFS) will be the time from randomization to documented progression or death. Individuals will be censored at the date of last evaluation for progression if neither event is observed. Overall survival will be defined as time from randomization until death from any cause. Participants will be censored at the date of last contact if the date of death is not observed. Local PFS will be the duration from randomization to local progression or death if death occurs before local progression. Metastasis free survival will be the duration from randomization to metastasis or death from any cause, if death occurs before metastasis. Individuals will be censored at the time of the last evaluation for local or distant progression, respectively, if neither progression nor death is observed.

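### Scheduled imaging ends at the first progression of either kind, so local PFS and metastasis-free survival are incompletely observed for patients whose other failure type comes first

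*Combined protocol and SAP*

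**What the plan says.** Three sections end on-study follow-up at the first progression of any type.

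- Section 7.4: "Patients will remain enrolled on this protocol until there is evidence that their disease has progressed either locally or distantly", or until withdrawal; then "These patients will be followed for survival".
- Section 7.5 lists "disease progression (as defined in Section 15.1.2 Disease Parameters") among the reasons for removal and adds: "Patients withdrawn from the study will be followed for overall survival only".
- Section 7.2 runs the later visit schedule, which includes the scans, "until death or study withdrawal (due to progression, patient withdrawal, or noncompliance as defined in Section 7.5 Criteria for Removal from Study").

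Section 15.1.5 defines two endpoints that look past one type of progression to the other.

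- The local endpoint: "Local PFS will be the duration from randomization to local progression or death if death occurs before local progression".
- The distant endpoint is built the same way, with the two failure types exchanged: "Metastasis free survival will be the duration from randomization to metastasis or death from any cause, if death occurs before metastasis".
- The censoring rule that applies to both endpoints: "Individuals will be censored at the time of the last evaluation for local or distant progression, respectively, if neither progression nor death is observed".

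Section 17.1.2 lists both as secondary comparisons between arms. Section 15.1.2 defines local and distant progression by CT and has them recorded separately. Section 17.4 names Kaplan-Meier curves and Cox models, gives no competing-risk method, and does not name local PFS in its list of time-to-event outcomes.

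**The concern.** Distant progression is not an event for local PFS, and local progression is not an event for metastasis-free survival. Each endpoint therefore needs CT to continue after the other failure has occurred, yet at that point the patient leaves the scan schedule. A later progression of the second type can be seen only by chance.

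This matters because local control is where SBRT is expected to act; section 2.3 presents it as the main potential benefit. If the missed events differ in number between arms, the comparison is biased as well as imprecise. The plan also leaves room for two handlings, counting the later death or censoring at the first progression, which can move the estimated effect in opposite directions.

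**Working it through.** **1. Is there a passage that restores the scans?** Four come close, and none does.

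- Section 7.2 follows patients until death only while they remain on study.
- Sections 5.3 and 7.1 keep PFS follow-up for patients who go off protocol because of treatment timing, not because of progression.
- Section 5.2 concerns progression before randomization.
- Section 15.1.2 records local and distant progression separately but does not extend imaging.

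**2. Does the primary design stand?** Section 17.3.2 gives medians of 6 and 10.2 months, 86 patients per arm, 60 months of accrual and at least 12 of follow-up. With λ = ln 2/median, expected events per arm are 86 × [1 − (e^(−12λ) − e^(−72λ))/(60λ)]. This gives 82.9 + 76.8 = 159.7, against 83 + 77 = 160 in section 17.5.2. Schoenfeld power is Φ(√160/2 × ln(10.2/6) − 1.96) = Φ(1.396), or 91.9%; Freedman's formula gives 90.6%; the plan states 91%. Primary PFS ends at first progression of either kind, so the gap does not touch it. The plan gives no figure for local PFS or metastasis-free survival.

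**3. Size under the written rule (illustration).**

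Assumptions:
- Local share q of first failures is 0.35 in control and 0.15 with SBRT.
- Hazards are exponential and independent, at the design medians.
- No patient dies without progression.
- Median survival after progression, m, is 4 or 8 months.

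Notation, per month: λ = ln 2/median, local hazard l = qλ, distant hazard h = (1 − q)λ, death hazard after progression d = ln 2/m.

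- Control: λ = 0.1155, l = 0.0404, h = 0.0751.
- SBRT: λ = 0.0680, l = 0.0102, h = 0.0578.
- d = 0.1733 (m = 4) or 0.0866 (m = 8).

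Share of patients with distant failure first and local progression unseen before death: (1 − q) × l/(l + d).

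- Control: 0.65 × 0.0404/0.2137 = 12.3% (m = 4); 0.65 × 0.0404/0.1271 = 20.7% (m = 8).
- SBRT: 0.85 × 0.0102/0.1835 = 4.7% (m = 4); 0.85 × 0.0102/0.0968 = 9.0% (m = 8).

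Local PFS at 12 months:

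- Full imaging: e^(−12λ) + h[e^(−12(l+d)) − e^(−12λ)]/(h − d).
- Scans stop at first progression, death is the event: e^(−12λ) + h[e^(−12d) − e^(−12λ)]/(λ − d).

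| m | Imaging | Control | SBRT | Difference |
|---|---|---|---|---|
| 4 | full | 0.3823 | 0.6083 | 22.6 points |
| 4 | stops | 0.4125 | 0.6165 | 20.4 points |
| 8 | full | 0.4604 | 0.7016 | 24.1 points |
| 8 | stops | 0.5192 | 0.7171 | 19.8 points |

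Control is overstated by 3.0 to 5.9 points and SBRT by about 0.8 to 1.5, so the difference shrinks by about 2 to 4 points.

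**4. A wider set of assumptions.** A simulation covered 24 scenarios:

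- local share of first progressions 30% or 50%;
- SBRT cause-specific hazard ratios (local/distant) of 0.3/0.8, 0.3/1.0 or 0.588/0.588;
- survival after progression 4 or 8 months;
- independent or correlated risks;
- 5% of the control first-event hazard being death without progression.

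Results:

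- Unseen local progression was 9-18% in control and 4-12% with SBRT, larger in control every time.
- With death as the event, the local PFS hazard ratio moved 0.01-0.07 toward 1 and the control median was overstated by 0.5-2.2 months. The metastasis-free survival hazard ratio moved 0.01-0.09 toward 1.
- With censoring at first progression and SBRT acting mainly locally, the local hazard ratio was 0.37-0.51, against 0.49-0.80 for full-imaging local PFS across all scenarios. The metastasis-free survival hazard ratio could move from 0.84 to 1.13.
- When both hazards fell equally, censoring changed the local hazard ratio little.

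**The case against.** Most of what these endpoints need is observed. A local progression that comes first is seen, and a death with no local progression before it is counted correctly. Section 15.1.5 makes death an event, so counting it is the stated definition. The loss is confined to progressions of the second type between the first progression and death. Only secondary endpoints are involved, and the site of first failure is already recorded. All of this stands, and a reader who infers that the two endpoints cannot be observed at all goes further than the text allows.

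A reader might also infer that the plan inflates the apparent local benefit of SBRT. With the same assumed shares, 12-month local failure as a first event is q(1 − e^(−12λ)): 26.2% against 8.4%, a gap of 18 points. Censoring every distant failure gives 1 − e^(−12λq): 38.4% against 11.5%, a gap of 27. The documents do not support that as the expected result. Section 15.1.5 censors only if no death is observed, and survival is still followed, so most patients with distant failure first will be counted at death. The two gaps also measure different quantities, and neither is local PFS. Nor does the inflation under censoring follow the arm with more distant-first failure. In this example it is larger in control (12 against 3 points), although SBRT has the larger distant share and the 12-month distant-first incidence is nearly equal (48.8% against 47.4%).

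**Conclusion.** The concern holds for patients whose other failure type comes first. Sections 7.2, 7.4 and 7.5 do not supply the imaging that section 15.1.5 requires, and no other section does. Followed as written, the plan makes local PFS times too long, more so in control, and tends to attenuate the SBRT effect. In the worked example the attenuation is from about 23-24 to about 20 points at 12 months. Exaggeration arises only if an analyst censors at distant progression instead and SBRT acts mainly locally.

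That arm-specific events are missed follows from the text together with any plausible local effect of SBRT. The size does not: the documents give no local/distant split, no effect by failure type and no survival after progression. Primary PFS, its 91% power and the interim analysis are untouched. The point should be settled before analysis, but it is not a threat to the main result.

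**What to change.** Reconcile sections 7.2, 7.4 and 7.5 with 15.1.5 and 17.1.2, and add to section 17.4:

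- Local and distant progression are each reported by arm as site-of-first-failure cumulative incidence, with the other failure type and death without progression as competing events.
- Cause-specific hazard ratios are reported alongside and interpreted as ratios of first-failure hazards. These models themselves censor at the competing failure. In the example the ratio is (0.15 × 6)/(0.35 × 10.2) = 0.25, the same as a Cox model that censors at distant progression. The gain therefore comes from the incidence curves and the stated limit on interpretation.
- Local PFS and metastasis-free survival are observed only to first progression.
- A rule is given for local and distant progression found on the same scan, and for clinical progression with no site.

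The data are already collected and no scan or visit is added, so the cost is a short amendment to the analysis plan. The downside is that this replaces the two endpoints rather than recovering them. The trial would support no conclusion on local control after distant failure, or on metastasis after local failure. It is a cheap improvement.

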7.5 Criteria for Removal from Study

Patients will be withdrawn from the study for any of the following reasons:

- disease progression (as defined in Section 15.1.2 Disease Parameters)
- patient withdrawal
- pregnancy
- patient noncompliance, or failure of the patient to follow instructions of the study staff
- protocol director decides that continuing participation could be harmful to the patient
- treatment needed for patient that is not allowed in the study
- patient is deemed resectable and proceeds to surgery
- study cancellation
- other administrative reasons
- unanticipated circumstances.

Patients will continue mFFX on-study until one of these endpoints; in the event of intolerable toxicity from mFFX, subjects will still be followed per protocol although chemotherapy may be altered or discontinued, the decisions of which will be left to the treating Medical Oncologist.

Patients withdrawn from the study will be followed for overall survival only.

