5.2 Restaging Following mFOLFIRINOX

After induction chemotherapy (up to 4 cycles), patients will have a CT scan for re-staging. Re-staging scans should be scheduled within 2 weeks following completion of induction mFOLFIRINOX. To allow for scheduling complications, outside sites may perform the simulation (SIM) scan during the final cycle of chemotherapy up to 4 weeks prior to start of treatment. If the subjects are randomized to the SBRT arm and the SIM was more than 4 weeks prior to treatment start date, a re-SIM will be performed to ensure that the plan is still appropriate for tumor treatment.

- If there is radiological or clinical evidence of disease progression, patient will not continue with the randomized portion of this study, but should be treated according to treating physician's discretion. (Based upon the study by Conroy *et al*, the progression-free survival at 3 months is estimated to be 75%; therefore the number of patients evaluated for the protocol and ultimately enrolled will be adjusted accordingly.) These patients will continue to be followed as part of the study.
- If a patient has radiologically responding or stable disease, s/he may proceed with randomization as described in the following section. Patients may undergo surgical resection at any time if clinically appropriate after surgical evaluation.

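### Section 7.5 ends progression follow-up for patients withdrawn before progression, although PFS is analysed in all randomized patients

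*Combined protocol and SAP*

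**What the plan says.** PFS is primary (1.1, 17.1.1), and 17.2 puts every randomized patient in the efficacy analysis. The follow-up rules differ from section to section.

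- **7.5** lists reasons for withdrawal. Several can precede progression: noncompliance, need for a treatment the study does not allow, a decision by the protocol director, administrative reasons, and "patient is deemed resectable and proceeds to surgery". It ends: "Patients withdrawn from the study will be followed for overall survival only".
- **6.1.3 item 8** withdraws from the study an SBRT patient whose plan cannot meet the fallback constraint, so 7.5 then applies.
- **7.2** says of resected patients: "These patients will be withdrawn from the protocol and followed for survival". Its visits for years 2 and 3 run "until death or study withdrawal (due to progression, patient withdrawal, or noncompliance as defined in Section 7.5 Criteria for Removal from Study". **7.4** keeps patients enrolled until progression "or until study withdrawal for any reason. These patients will be followed for survival". Both name survival follow-up, but without the word *only*.
- **5.2** allows surgery in either arm: "Patients may undergo surgical resection at any time if clinically appropriate after surgical evaluation".
- **6.2** sends a patient who cannot keep the SBRT schedule off protocol, names overall survival as what is followed, and promises an intention-to-treat analysis.
- **5.3** (both arms) and **7.1** keep overall survival and PFS follow-up when the 8-week limit is exceeded. For intolerable mFFX toxicity, 7.2 and 7.5 say "subjects will still be followed per protocol although chemotherapy may be altered or discontinued".
- **15.1.5** ends PFS at documented progression or death and censors at the last progression evaluation when neither is observed. **15.1.2** defines local progression as growth of at least 20% from the pre-chemotherapy CT.

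**The concern.** A patient resected or withdrawn while progression-free must be in the primary analysis, yet 7.5 stops the collection of the data that analysis needs. The plan already separates leaving treatment from leaving follow-up in 5.3, 7.1 and the toxicity clause, but does not do so elsewhere. Two of the rules (planning failure in 6.1.3 item 8 and SBRT-schedule failure in 6.2) can act only in the SBRT arm, so the loss need not be balanced.

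At stake are the hazard ratio, the type 1 error and the power of the primary comparison. Scans that are never collected cannot reliably be recovered at analysis.

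**Working it through.** **1. The plan's own figures.** Inputs from 17.3.2: medians 6 and 10.2 months, 86 per arm, 60 months of accrual, at least 12 months of follow-up, exponential PFS, two-sided 0.05. With L = ln 2 / median,

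P(event) = 1 − [exp(−12L) − exp(−72L)] / (60L).

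- Control: L = 0.1155; P = 1 − (0.2500 − 0.0002)/6.931 = 0.964; 86 × 0.964 = 82.9 events.
- SBRT: L = 0.0680; P = 1 − (0.4424 − 0.0075)/4.077 = 0.893; 86 × 0.893 = 76.8 events.
- Total 159.7; 17.5.2 states 83 + 77 = 160.
- Power (Schoenfeld), HR = 6/10.2 = 0.588: Φ(√160 × 0.531/2 − 1.96) = Φ(1.40) = 91.9%. Freedman's formula gives 90.6% and simulation 91.2%. The plan states 91%.

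These agree only when no progression data are lost, so the design makes no allowance for such loss.

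**2. The follow-up rules side by side.**

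| Situation | Section | Follow-up named |
|---|---|---|
| Over 8 weeks between treatments, either arm | 5.3 | OS and PFS |
| Chemotherapy not resumed within 8 weeks of SBRT | 7.1 | OS and PFS |
| Intolerable mFFX toxicity | 7.2, 7.5 | per protocol |
| SBRT schedule not kept | 6.2 | OS |
| Resection | 7.2, 7.5 | survival; OS only in 7.5 |
| Planning constraint not met | 6.1.3(8), then 7.5 | OS only |
| Noncompliance, disallowed treatment, investigator decision, administrative | 7.5 | OS only |

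An SBRT patient over the 8-week limit between induction and SBRT falls under both 5.3 and 6.2, which name different follow-up. The trigger in 7.1 is a different one.

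**3. What happens to the PFS event.** Survival is still followed, so a later death is observed. Under 15.1.5 it is then the event; 17.3.2 and 17.5.2 are consistent with that. Progression without scans is therefore replaced by a later death. If survival after progression has a median of 5 or 8 months (assumed), the mean delay is 5/0.693 = 7.2 or 8/0.693 = 11.5 months, against a mean control PFS of 6/0.693 = 8.7 months.

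**4. Size.** Monte Carlo with the design inputs above, Cox HR and log-rank test at |z| > 1.96. Assumptions: loss at month 1, earlier progression still recorded, the later death counted. Ranges cover the 5- and 8-month assumption and simulation error. All loss rates are assumed; 5% of an arm is 0.05 × 86 = 4.3 patients.

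| Scenario | HR | Result |
|---|---|---|
| No true effect, no loss | 1.00 | about 2.5 to 3% error each way |
| 2% SBRT only | 0.98 to 0.99 | 3.1 to 3.7% favouring SBRT |
| 5% SBRT only | 0.94 to 0.96 | 4.5 to 5.7% favouring SBRT |
| 10% SBRT, 5% control | 0.95 to 0.97 | 4.3 to 5.6% favouring SBRT |
| 10% control, 5% SBRT | 1.04 to 1.05 | 4.6 to 5.4% favouring control |
| Equal 5% or 10% | 1.00 | no bias under the null |
| Planned effect, no loss | 0.585 | power about 91% |
| Planned effect, equal 10% | 0.60 to 0.61 | power about 87 to 89% |

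The lower end of the 2% row is hardly distinguishable from the no-loss runs.

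**5. After resection.** A removed lesion cannot grow by 20%, so the local rule in 15.1.2 fails. Disease outside the pancreas (15.1.2, 15.1.3), the clinical criteria in 7.4 and death still apply. A recurrence in the tumour bed has no clear category.

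**The case against.** The strongest reply is that little is lost. Progression, the first reason in 7.5, is itself the PFS event. Withdrawal of consent may properly end assessment. Some noncompliant patients would not attend scans anyway. SBRT-only losses are probably few: 6.1.3 item 8 has a fallback before withdrawal, 3.1 ties eligibility to the constraints, and 5.2 provides that "a re-SIM will be performed to ensure that the plan is still appropriate for tumor treatment". Sections 5.3, 6.2 and 7.1 already promise intention-to-treat analysis. All of this stands. It limits the numbers but does not remove the conflict or restore data that 7.5 says will not be followed.

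Some stronger readings are tempting but unsupported:

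- *That these patients are censored and their events lost.* As written, a known death counts. Censoring at the last evaluation is an alternative rule. It matters as a sensitivity analysis: if patients with half the hazard are resected at month 3, 10% in the SBRT arm against 5% in control, with no true effect, the HR is 0.96 to 0.97 when late death counts and about 1.04 when censored (rates assumed).
- *That equal loss is harmless.* With late deaths counted, this holds only under the null.
- *That 7.2, 7.4 and 6.2 forbid progression follow-up.* They name survival without excluding the rest; only 7.5 excludes it. The direct conflict of 6.2 is with 5.3, not 7.1.
- *That recurrence after resection is wholly undefined.* Only the size rule fails.

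**Conclusion.** The point holds. For patients withdrawn before progression, 7.5 ends the follow-up that the primary analysis in 17.2 requires, and 6.2 and 5.3 give different follow-up for an overlapping case. As the plan is written, the effect is mainly late dating of PFS events.

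On assumed rates, an imbalance of about 5 percentage points shifts the null hazard ratio by roughly 0.03 to 0.06, and the one-sided error in the favoured direction rises to about 4.3 to 5.7%. Equal 10% loss costs about 2 to 4 points of power under the planned effect.

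A reader might infer that the result will be biased towards SBRT. The documents do not support that: they give no loss or resection rates, resection can occur in either arm, and the reverse imbalance favours control. Size and direction are unknown. The matter should be fixed because the gap concerns the primary endpoint and closing it is cheap.

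**What to change.** - Reconcile the follow-up wording of 6.1.3 item 8, 6.2, 7.2, 7.4 and 7.5 with 5.3 and 7.1. For every randomized patient who has not withdrawn consent to follow-up, collect routine scan dates and reports until progression or death, whatever treatment is being given.
- In 15.1.5, state how recurrence after resection counts as a PFS event, including recurrence in the tumour bed.
- In 15.1.5, state expressly that a known death after missed progression assessments is the event, as the current wording implies. Add a sensitivity analysis that censors such patients at the last evaluation.
- Report by arm how many patients lost progression follow-up and why, with resections shown separately.

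The cost is an amendment and the collection of routine scan reports for patients off protocol treatment. Nobody's treatment changes.
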